4.5.12.6 Withdrawal from the Research Biosample Repository

Patients who give consent to provide RBR specimens have the right to withdraw their consent at any time for any reason. *After withdrawal of consent, any remaining samples will be destroyed or will no longer be linked to the patient.* However, if RBR specimens have been tested prior to withdrawal of consent, results from those tests will remain as part of the overall research data. If a patient wishes to withdraw consent to the testing of his or her specimens, the investigator must inform the Medical Monitor in writing of the patient's wishes through use of the appropriate RBR Subject Withdrawal Form and, if the trial is ongoing, must enter the date of withdrawal on the RBR Research Sample Withdrawal of Informed Consent eCRF. The patient will be provided with instructions on how to withdraw consent after the trial is closed. A patient's withdrawal from Study GN39763 does not, by itself, constitute withdrawal of specimens from the RBR. Likewise, a patient's withdrawal from the RBR does not constitute withdrawal from Study GN39763.

If a patient wishes to withdraw consent to the testing of his or her specimens after closure of the site, the investigator must inform the Sponsor by emailing the study number and patient number to the following email address:

[contact]

4.5.12.7 Monitoring and Oversight

RBR specimens will be tracked in a manner consistent with Good Clinical Practice by a quality-controlled, auditable, and appropriately validated laboratory information management system, to ensure compliance with data confidentiality as well as adherence to authorized use of specimens as specified in this protocol and in the Informed Consent Form. Sponsor monitors and auditors will have direct access to appropriate parts of records relating to patient participation in the RBR for the purposes of verifying the data provided to the Sponsor. The site will permit monitoring, audits, IRB/EC review, and health authority inspections by providing direct access to source data and documents related to the RBR samples.

4.6 TREATMENT, PATIENT, STUDY, AND SITE DISCONTINUATION

4.6.1 Study Treatment Discontinuation

Patients must permanently discontinue study treatment if they experience any of the following:

- Any medical condition that the investigator or Sponsor determines may jeopardize the patient's safety if he or she continues to receive study treatment
- Investigator or Sponsor determines it is in the best interest of the patient
- Pregnancy

The primary reason for study treatment discontinuation should be documented on the appropriate eCRF. Patients who discontinue study treatment prematurely will not be replaced.

Patients will return to the clinic for a treatment discontinuation visit 12 weeks (± 7 days) after the last dose of study drug (see [Appendix 1](#) and [Appendix 2](#) for additional details).

4.6.2 Patient Discontinuation from Study

Patients have the right to voluntarily withdraw from the study at any time for any reason. In addition, the investigator has the right to withdraw a patient from the study at any time. Reasons for withdrawal from the study may include, but are not limited to, the following:

- Patient withdrawal of consent
- Study termination or site closure
- Patient non-compliance, defined as failure to comply with protocol requirements as determined by the investigator or Sponsor

Every effort should be made to obtain information on patients who withdraw from the study. The primary reason for withdrawal from the study should be documented on the appropriate eCRF, as well as in the site source document. Patients who withdraw from the study will not be replaced.

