Appendix 1 Schedule of Activities (cont.)

- i Only perform assessment if discontinuation visit is ≥ 16 weeks after last assessment for this instrument or procedure. However, if the patient discontinues study drug because of an infusion-related reaction, concurrent ADA and PK samples will also be collected at 12 weeks after the last administration of study drug.
- j Includes respiratory rate, pulse rate, and systolic and diastolic blood pressure while the patient is in a seated position, and temperature. Record abnormalities observed at baseline on the General Medical History and Baseline Conditions eCRF. At subsequent visits, record new or worsened clinically significant abnormalities on the Adverse Event eCRF. On study drug treatment visits, vital signs should be collected 0–4 hours prior to infusion and 60–90 minutes after completion of infusion.
- k Vital signs should be assessed on the same day(s) that the [^{18}F]GTP1 PET scan and/or LP are performed. Vital signs should be assessed just prior to injection of [^{18}F]GTP1 or initiation of the LP procedure, but no earlier than 1 hour prior to injection of [^{18}F]GTP1 or initiation of the LP procedure. Vital signs should also be assessed just after injection of [^{18}F]GTP1 or conclusion of the LP procedure, but no later than 1 hour after injection of [^{18}F]GTP1 or conclusion of the LP procedure.
- l Includes evaluation of the head, eyes, ears, nose, and throat, and the cardiovascular, dermatological, respiratory, and gastrointestinal systems. In addition, the musculoskeletal and genitourinary systems should be examined as clinically indicated. Record abnormalities observed at baseline on the General Medical History and Baseline Conditions eCRF. At subsequent visits, record new or worsened clinically significant abnormalities on the Adverse Event eCRF.
- m Perform a limited, symptom-directed examination at specified timepoints or as clinically indicated. Record new or worsened clinically significant abnormalities on the Adverse Event eCRF.
- n If amyloid PET is used to confirm amyloid positive eligibility, an LP will not be performed as part of screening. If amyloid PET result suggests a patient is amyloid negative, an LP may be performed as part of screening to re-assess amyloid positivity eligibility on the basis of CSF.

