4.4.1 Primary Efficacy Endpoint

The primary efficacy objective for this study is to evaluate the efficacy of MTAU9937A compared with placebo on the basis of CDR-SB change from baseline at Week 73 (with baseline defined as the average of available measurements before first dose which is expected to include both screening and baseline values).

The estimand of interest (the mITT estimand) is the mean absolute difference in CDR-SB change from baseline at Week 73 between active drug and placebo. It will be estimated using all randomized patients who received at least one dose of study drug, regardless of adherence to the assigned study treatment or to the protocol.

The MMRM approach described in Section 4.4 should provide a reasonable estimate of the mITT estimand. Mean change from baseline will be estimated at each post-baseline timepoint for each study arm (placebo and each treatment arm) using least squares means and 95% confidence intervals. The absolute difference in mean change from baseline will be estimated for each treatment arm compared with placebo using least-squares mean estimates from the MMRM model along with 95% confidence intervals.

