4.6 MISSING DATA

A careful examination of reasons for study discontinuation will be conducted to assess the nature of incomplete data. In addition, frequencies and percentages of missing data at Week 73 will be compared between the two treatment arms. Missing data will not be imputed for the

primary analysis, but will instead be handled via the missing-at-random (MAR) assumption from the MMRM model as described in Section 4.4. Analyses to explore the sensitivity of results to missing data assumptions will be conducted as described in section 4.4.3. The issue of missing data for secondary and exploratory endpoints will be handled similarly with a MMRM model.

Patients who discontinue the study will be included in the analysis up to the date of study discontinuation.

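### Protocol 4.6.2 permits withdrawal from the study for non-compliance, which can lose Week 73 CDR-SB values that the SAP's primary analysis wants regardless of adherence

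*Protocol*

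**What the plan says.** Protocol 4.6.1 covers stopping study treatment. Section 4.6.2 covers leaving the study. In 4.6.2, "the investigator has the right to withdraw a patient from the study at any time", and a non-exhaustive list of possible reasons includes "Patient non-compliance, defined as failure to comply with protocol requirements as determined by the investigator or Sponsor". No threshold is given. The right to withdraw belongs to the investigator; the Sponsor is named only as able to judge non-compliance. The same section adds: "Every effort should be made to obtain information on patients who withdraw from the study".

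SAP 4.4.1 says the estimand "is the mean absolute difference in CDR-SB change from baseline at Week 73 between active drug and placebo", to be estimated in all randomised patients who received at least one dose, "regardless of adherence to the assigned study treatment or to the protocol". SAP 4.6 says: "Patients who discontinue the study will be included in the analysis up to the date of study discontinuation". Missing values are not imputed for the "primary analysis, but will instead be handled via the missing-at-random (MAR) assumption from the MMRM model as described in Section 4.4". SAP 4.4.3 adds completer, linear extrapolation, last-observation-carried-forward and tipping point analyses.

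Under Protocol 4.6.1 and Appendix 1, a patient who stops study drug early has one visit 12 weeks after the last dose. For the CDR at that visit the footnote reads: "Only perform assessment if discontinuation visit is ≥ 16 weeks after last assessment for this instrument or procedure".

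**The concern.** Failure to follow the protocol is something the primary analysis is meant to look past. It is also a listed reason for ending the follow-up that the analysis depends on. A patient who misses visits or infusions but is willing to be assessed can be taken out of the study, and the Week 73 CDR-SB is then lost by decision and not by necessity.

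The MMRM fills the gap implicitly. It treats the withdrawn patient as someone who would have followed the course of patients in the same arm with similar earlier scores and covariates who stayed. That is closer to asking what would have happened had the patient remained in the study than to an effect regardless of adherence. In prodromal to mild Alzheimer's disease it is plausible, though the documents do not say so, that missed visits track decline or caregiver strain. In that case earlier CDR-SB scores may not fully explain the missingness.

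**Working it through.** **Step 1. Passages side by side.**

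| Question | Document and section | Answer |
|---|---|---|
| Can non-compliance end study participation? | Protocol 4.6.2 | Yes, by permission; judged by investigator or Sponsor |
| Whose outcomes does the primary estimate draw on? | SAP 4.4.1 | All dosed patients, whatever their adherence |
| Are data after study discontinuation used? | SAP 4.6 | No, only data up to that date |
| Is a Week 73 CDR scheduled for a withdrawn patient? | Protocol 4.6.2, Appendix 1 | No |

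Two details follow.

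- The early-discontinuation visit falls at Week 73 only if the last dose was at Week 61 (61 + 12 = 73), so it does not generally replace the Week 73 assessment.
- SAP 4.1.1 requires at least one post-baseline CDR-SB. A patient withdrawn before any such measurement drops out of the efficacy population, and the MMRM cannot recover that patient.

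**Step 2. Reproduce the plan's own figures.** Inputs from SAP 2.2: difference 0.6, SD 2, dropout 25%, 228 patients (4500 mg and 8100 mg pooled) against 137 (placebo) before dropout. SAP 4.4 sets a two-sided 5% level.

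- Retained: 228 × 0.75 = 171.0 and 137 × 0.75 = 102.75.
- SE = 2 × √(1/171.0 + 1/102.75) = 0.2496.
- Power = Φ(0.6/0.2496 − 1.960) = Φ(0.443) = 67.1% (66.8% with the noncentral t). The SAP states 68%, so this agrees within about a point.
- 90% interval for 4500 mg against placebo: n per arm = 457 × 0.3 × 0.75 = 102.8; SE = 2 × √(2/102.8) = 0.279; 0.6 ± 1.645 × 0.279 = 0.14 to 1.06, as in the SAP. With 360 patients, n = 81 and SE = 0.314, giving 0.08 to 1.12, as in the protocol.

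The planning figures are not in error.

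**Step 3. Illustrate the size.** The documents give no non-compliance withdrawal rate. Assume that a share x of randomised patients, lying inside the 25% dropout, is withdrawn for this reason and could instead be followed to Week 73. The retained fraction becomes 0.75 + x, with the effect held at 0.6.

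| x (assumed) | Patients of 457 | Retained, pooled / placebo | Power |
|---|---|---|---|
| 0% | 0 | 171.0 / 102.8 | 67.1% |
| 1% | 4.6 | 173.3 / 104.1 | 67.7% |
| 2% | 9.1 | 175.6 / 105.5 | 68.3% |
| 5% | 22.9 | 182.4 / 109.6 | 69.9% |
| 10% | 45.7 | 193.8 / 116.5 | 72.5% |

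For bias, one further assumption gives a sense of scale. Suppose withdrawn active patients gain no benefit while the missing-at-random model credits them with the full 0.6. The overstatement is 0.6 × x: 0.006 points at 1%, 0.012 at 2%, 0.03 at 5% and 0.06 at 10%. Neither x nor the absence of benefit comes from the documents.

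**The case against.** The strongest reply is that the plan already leans the right way.

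- The list in 4.6.2 is permissive, so most non-adherent patients need never be withdrawn.
- The adherence phrase in SAP 4.4.1 sits in the sentence about which patients are used, not in the definition of the estimand. Reading it as a treatment-policy estimand is an inference.
- For patients who start prohibited medication, Protocol 4.1.2 speaks of withdrawal from study treatment, not from the study. Patients who move into a care facility may continue to be followed for efficacy if they have a suitable caregiver.
- SAP 4.4.3 sets data after missed doses or changes in symptomatic medication to missing only in sensitivity analyses, so the primary analysis expects such data to exist.
- Deviations are already documented and summarised by arm (Protocol 9.2, SAP 4.2).

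All of this stands, and it limits the point. It does not remove it. An estimate at Week 73 that includes non-adherent patients needs their Week 73 values or an assumption in their place. Follow-up information gathered after withdrawal names no CDR visit, and SAP 4.6 would not use it. A tipping point analysis tests the assumption but does not replace the outcome.

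Two stronger readings are tempting. A reader might infer that the plan requires non-compliant patients to be removed and discards their data. It does not: withdrawal is discretionary, and data before withdrawal stay in the model. A reader might also infer material bias in the treatment effect. That would need a withdrawal rate, together with a difference between arms or a lack of benefit in those withdrawn, and the documents give none of these.

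One practical limit also stands. The CDR needs a caregiver informant (Protocol 4.5.7.2), so where non-compliance reflects the loss of the caregiver, the assessment may be unobtainable.

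**Conclusion.** The inconsistency is real but narrow. Protocol 4.6.2 allows follow-up to end for a reason that SAP 4.4.1 says should not matter, and SAP 4.6 closes the data at that date. Each such withdrawal of a patient who would have stayed is an avoidable missing primary outcome resting on the missing-at-random assumption.

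The size cannot be determined from the documents and is probably small. At an assumed 5% of randomised patients, retention would be worth just under 3 points of power (67.1% to 69.9%). That illustration assumes these patients lie within the 25% dropout, could all be followed to Week 73, and leave the 0.6-point effect unchanged. This is a cheap improvement to the plan; it does not show the primary analysis to be invalid.

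**What to change.** - **Protocol 4.6.2:** remove non-compliance from the reasons for withdrawal from the study. State that non-compliance alone is recorded as a protocol deviation, and that patients who still consent continue the scheduled CDR and other clinical outcome assessments through Week 73, whether or not they remain on study drug. Align the Appendix 1 discontinuation footnotes with this.
- **SAP 4.4.1 and 4.6:** state that outcomes collected after non-compliance, through Week 73, enter the primary analysis.

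The list in 4.6.2 is open-ended, so deleting the bullet alone would change little; the positive statement about continued assessment does the work. The investigator's general right to withdraw a patient for other reasons can stay, and the rules in 4.6.1 on stopping study drug are untouched.

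The cost is a protocol bullet, a footnote alignment, an SAP sentence and an instruction to sites, which would keep scheduling outcome visits for a few poorly compliant patients. Enrolment is complete at 457, so only patients still in the double-blind period would benefit.

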4.6.3 Study Discontinuation

The Sponsor has the right to terminate this study at any time. Reasons for terminating the study may include, but are not limited to, the following:

- The incidence or severity of adverse events in this or other studies indicates a potential health hazard to patients
- Patient enrollment is unsatisfactory

The Sponsor will notify the investigator if the Sponsor decides to discontinue the study.

4.6.4 Site Discontinuation

The Sponsor has the right to close a site at any time. Reasons for closing a site may include, but are not limited to, the following:

- Excessively slow recruitment
- Poor protocol adherence
- Inaccurate or incomplete data recording
- Non-compliance with the International Council for Harmonisation (ICH) guideline for Good Clinical Practice
- No study activity (i.e., all patients have completed the study and all obligations have been fulfilled)

5. ASSESSMENT OF SAFETY

5.1 SAFETY PLAN

MTAU9937A is not approved, and clinical development is ongoing. The safety plan for patients in this study is based on clinical experience with MTAU9937A in completed and ongoing studies. Important potential safety risks for patients receiving MTAU9937A are outlined below. Refer to the MTAU9937A Investigator's Brochure for a complete summary of safety information.

[¹⁸F]GTP1 is not approved by any health authority, and clinical development is ongoing. The safety plan for participants in this study is based on clinical experience with [¹⁸F]GTP1 in completed and ongoing studies, and the safety experience to date is detailed in the [¹⁸F]GTP1 Investigator's Brochure.

Several measures will be taken to ensure the safety of patients participating in this study. Eligibility criteria have been designed to exclude patients at higher risk for toxicities. Patients will undergo safety monitoring during the study, including assessment of the nature, frequency, and severity of adverse events. Ongoing review of unblinded safety will be performed by an iDMC (see Section 3.1.2). External experts may be consulted. In addition, guidelines for managing adverse events, including criteria for dosage modification and treatment interruption or discontinuation, are provided below.

5.1.1 Potential Risks Associated with MTAU9937A

5.1.1.1 Infusion-Related Reactions or Hypersensitivity

Monoclonal antibodies such as MTAU9937A may be associated with a potential immune response in clinical trials, such as hypersensitivity or hypersensitivity-like reactions, including severe, anaphylactic reactions (see Appendix 5 for precautions). Study sites will be prepared to manage any hypersensitivity or hypersensitivity-like events.

All participants will be monitored for infusion reactions, hypersensitivity, or hypersensitivity-like reactions during the infusion and immediately afterwards (see Section 5.1.3.2 for additional instructions on monitoring and management of infusion reactions).

5.1.1.2 Neuroimaging Abnormalities

The occurrence of imaging abnormalities believed to represent cerebral vasogenic edema and microhemorrhage have been reported in association with the investigational use of immunotherapy targeting the A β peptide, possibly by interacting with A β deposited in or around blood vessels and eliciting an immune response. Symptoms, when present in association with such imaging abnormalities, have been reported to include headache, worsening cognitive function, alteration of consciousness, seizures, unsteadiness, and vomiting (Salloway et al. 2009; Sperling et al. 2012).

Tau pathology occurs primarily intracellularly in the cytoplasm of diseased neurons (Braak et al. 2006), and soluble extracellular tau is found in the CSF (Blennow and Zetterberg 2009). Unlike A β , tau is not known to deposit in vascular structures, and administration of an antibody against the tau protein is not anticipated to cause vasogenic edema or microhemorrhage. Moreover, MTAU9937A has an IgG4 backbone, which is associated with reduced effector function. Nevertheless, in this study, the following will be performed to monitor for potential neuroimaging abnormalities:

- All patients will have an MRI at screening and at several postbaseline timepoints (see [Appendix 1](#) and [Appendix 2](#)). *MRI must be performed prior to any dosing on the corresponding study visit and must be read locally in real time for the evaluation of any new, clinically significant abnormality prior to the dose being given. However, if no such abnormalities are identified in the local MRI interpretation, the dose may be given prior to the receipt of the central MRI report. In case of an abnormality identified by the central MRI reading, the investigator should assess the clinical significance of it and proceed as described below.*
- Regardless of severity, all events of a clinically significant *new or worsening* MRI abnormality that occur at any time after receiving study drug are considered to be adverse events of special interest and *must* be reported in an expedited manner.
- All patients will regularly undergo neurologic examinations to evaluate for any neurologic signs or symptoms. In case of findings suggestive of a new, clinically significant central nervous system disturbance or lesion, patients must undergo an MRI examination *as soon as possible*.
- All MRIs will be read *locally* in real time for the evaluation of any clinically significant *new or worsening* abnormality. Study drug will be withheld *at the corresponding study visit if, in the investigator's judgment, any clinically significant new or worsening MRI abnormality (e.g., symptomatic or asymptomatic intracranial tumor, cerebral infarct [lacunar or territorial], cerebral hemorrhage [macrohemorrhage, microhemorrhage, superficial siderosis], vasogenic edema, sulcal effusion) is observed*. Restarting study drug treatment can occur only after discussion with the Medical Monitor.

5.1.1.3 Immunogenicity

MTAU9937A is a pan-tau IgG4 monoclonal antibody engineered to contain Fc mutations (YTE) that enhance binding to FcRn and have been shown to slow peripheral antibody clearance in humans. ADAs to MTAU9937A in humans may be associated with changes in MTAU9937A exposure, reductions in treatment efficacy, or safety findings such as hypersensitivity reactions. There was no evidence of treatment emergent ADA in the ongoing Phase I study (GN39058). Immunogenicity in humans will be evaluated using validated immunoassays and by assessing the incidence of ADAs after treatment relative to their prevalence at baseline. The study site will be prepared to manage any hypersensitivity events.

Refer to Section 5.6 of the MTAU9937A Investigator's Brochure for ADA data from clinical trials.

5.1.2 Potential Risks Associated with [¹⁸F]GTP1 and Amyloid PET Radiopharmaceuticals

5.1.2.1 Infusion-Related Reactions

All participants will be monitored for infusion reactions both during the infusion and immediately afterwards. Infusion reactions should be treated as per institutional guidelines. In the event that a participant experiences an infusion-related reaction, the infusion should be halted.

